4.2 Event Monitoring

CRF	Event Monitoring Phase ¹				
	q. 3 months until PD	At PD ²	After PD q. 6 mos.	Death	New Primary
Event Monitoring	X	X	X	X	At each occurrence

1. If a patient is still alive 5 years after registration, no further follow-up is required.
2. Submit copy of documentation of response or progression by uploading it into the Supporting Documentation form in the Rave system.

5.0 Stratification Factors: None

6.0 Registration Procedures

6.1 Registering a patient

To register a patient, access the Mayo Clinic Cancer Center (MCCC) web page and enter the registration/randomization application. The registration/randomization application is available 24 hours a day, 7 days a week. Back up and/or system support contact information is available on the Web site. If unable to access the Web site, call the MCCC Registration Office at [REDACTED] between the hours of 8 a.m. and 4:30 p.m. Central Time (Monday through Friday).

The instructions for the registration/randomization application are available on the MCCC web page [REDACTED] and detail the process for completing and confirming patient registration. Prior to initiation of protocol treatment, this process must be completed in its entirety and a MCCC subject ID number must be available as noted in the instructions. It is the responsibility of the individual registering the patient to confirm the process has been successfully completed prior to release of the study agent. Patient registration via the registration/randomization application can be confirmed in any of the following ways:

- Contact the MCCC Registration Office [REDACTED]. If the patient was fully registered, the MCCC Registration Office staff can access the information from the centralized database and confirm the registration.
- Refer to “Instructions for Remote Registration” in section “Finding/Displaying Information about A Registered Subject.”

6.2 Correlative Research

A mandatory correlative research component is part of this study, the patient will be automatically registered onto this component (see Sections 3.19b, 14.0 and 17.0).

6.3 Documentation required

Documentation of IRB approval must be on file in the Registration Office before an investigator may register any patients.

In addition to submitting initial IRB approval documents, ongoing IRB approval documentation must be on file (no less than annually) at the Registration Office (fax: [REDACTED]). If the necessary documentation is not submitted in advance of attempting patient registration, the registration will not be accepted and the patient may not be enrolled in the protocol until the situation is resolved.

When the study has been permanently closed to patient enrollment, submission of annual IRB approvals to the Registration Office is no longer necessary.

6.4 Verification

Prior to accepting the registration, registration application will verify the following:

- IRB approval at the registering institution
- Patient eligibility
- Existence of a signed consent form
- Existence of a signed authorization for use and disclosure of protected health information

6.5 Correlative research options

At the time of registration, the following will be recorded:

- Patient has/has not given permission to store and use his/her sample(s) for future research of lymphoma at Mayo.
- Patient has/has not given permission to store and use his/her sample(s) for future research to learn, prevent, or treat other health problems.
- Patient has/has not given permission for MCCC to give his/her sample(s) to researchers at other institutions.

6.6 Treatment start

Treatment cannot begin prior to registration and must begin ≤ 7 days after registration.

6.7 Pretreatment tests/procedures

Pretreatment tests/procedures (see [Section 4.0](#)) must be completed within the guidelines specified on the test schedule.

6.8 Baseline symptoms

All required baseline symptoms (see Section 10.6) must be documented and graded.

6.9a Treatment location

Treatment on this protocol must commence at Mayo Clinic Rochester, Mayo Clinic Arizona, or Mayo Clinic Florida institutions under the supervision of a hematologist.

6.9b Study drug availability

Study drug is available on site for this patient

6.9c Blood draw kits

Blood draw kit is available on site for this patient (not applicable to MCR).

7.0 Protocol Treatment

7.1 Treatment Schedule

7.11 Treatment Schedule

Agent	Dose Level	Route	Day	Cycle Length
Nivolumab	240mg	IV	Cycles 1-8 Day 1	Every 14 days for 8 cycles
	480 mg	IV	Beginning Cycle 9, Day 1	Every 28 days for a maximum of 24 cycles (Total of 32 cycles)

No routine premedications are needed with nivolumab administration.

7.2 Return to consenting institution

For this protocol, the patient must return to the consenting institution for evaluation at least every 14 days during initial treatment and every 28 days during continuation therapy.

After therapy discontinuation, the patient must return to the institution for four visits: 1) 35±7 days after last treatment; 2) 100-120 days post treatment; 3) 230-250 days post treatment; and 4) 330-390 days post treatment, during observation (Active Monitoring Phase) until the patient goes to event monitoring per Section 13.0.

8.0 Dose Delay Criteria Based on Adverse Events

For events with an attribution of possibly, probably or definitely related to study medication, strictly follow the modifications in this table for the first **two** cycles, until individual treatment tolerance can be ascertained. Thereafter, these modifications should be regarded as guidelines. If multiple adverse events are seen, administer dose based on greatest reduction required for any single adverse event observed. Reductions or increases apply to treatment given in the preceding cycle and are based on adverse events observed since the prior dose.

ALERT: ***ADR reporting may be required for some adverse events (See Section 10)***

8.1 No dose reductions or escalations are allowed for nivolumab.

8.2 Dose Delay Criteria for Nivolumab

See Management Algorithms ([Appendix II](#))

→ → Use the NCI Common Terminology Criteria for Adverse Events (CTCAE) version 4.0* unless otherwise specified ← ←

CTCAE System/Organ/Class (SOC)	Event	Agent	Action
Investigations	Alanine aminotransferase increased, Aspartate aminotransferase increased, and/or Blood bilirubin increased	Nivolumab	
If a patient has a baseline AST/ALT that is within the normal limits, delay dosing for nivolumab-related \geqGrade 2 (>3-5 x ULN) elevations and start corticosteroids at 0.5 to 1 mg/kg/day prednisone equivalents. Nivolumab may be resumed if the value improves to Grade 1 (≤ 3 x ULN) or better.
 
If a patient has a baseline AST/ALT in the Grade 1 range (ULN to ≤ 3 x ULN), delay dosing for nivolumab-related \geqGrade 3 (>5 to 8 x ULN) elevations and start corticosteroids at 1 to 2 mg/kg/day prednisone equivalents. Nivolumab may be resumed if the value improves to Grade 2 (>3 to 5 x ULN) or better.
 
If a patient has a baseline total bilirubin that is within normal limits, delay dosing for nivolumab-related Grade 2 elevations (>1.5-3 x ULN) and start corticosteroids at 0.5 to 1 mg/kg/day prednisone equivalents. Nivolumab may be resumed if the bilirubin improves to Grade 1 (≤ 1.5 x ULN) or better.
 
If a patient has a baseline total bilirubin that is in the Grade 1 range (ULN to ≤ 1.5 x ULN), delay dosing for nivolumab-related Grade 3 elevations (>3-5 x ULN) and start corticosteroids at 1 to 2 mg/kg/day prednisone equivalents.

CTCAE System/Organ/Class (SOC)	Event	Agent	Action
			
Nivolumab may be resumed if the total bilirubin improves to Grade 2 ($\leq 3 \times$ ULN) or better.
 
Doses of nivolumab should be discontinued permanently for the following LFT abnormalities: AST or ALT $>8 \times$ ULN (Grade 3) or drug-induced liver injury (DILI); Total bilirubin $>5 \times$ ULN (Grade 3) or DIL; concurrent AST or ALT $>3 \times$ ULN and total bilirubin $>2 \times$ ULN. Administer corticosteroids 1 to 2 mg/kg/day prednisone equivalents.
 
Subjects with combined Grade 2 AST/ALT meeting discontinuation parameters: go to event monitoring per Section 4.2.

Gastrointestinal disorders	Pancreatitis	Nivolumab	
Grade 2: Hold nivolumab until resolution, maximum 3 weeks.
 
If >3 weeks, discontinue nivolumab and patient goes to event monitoring.
 
Grade 3 or Grade 4, hold nivolumab until Grade 2 or better then reintroduce
 
If it recurs, the drug is discontinued and patient goes to event monitoring
 
Any \geqGrade 3 drug-related amylase or lipase abnormality that is not associated with symptoms or clinical manifestations of pancreatitis does not require dose delay
 
The PI should be consulted for \geqGrade 3 amylase or lipase abnormalities

Gastrointestinal disorders	Diarrhea	Nivolumab	
Grade ≥ 2 despite maximal supportive care: Hold drug until resolution to baseline grade. If suspicious and clinically indicated, initiate work up to rule out infectious causes and colitis
 
Grade 3 or 4 despite maximal supportive care: Discontinue drug and start corticosteroids until resolution to baseline and patient goes to event monitoring. If suspicious and clinically indicated, initiate work up to rule out infectious causes and colitis

	Colitis	Nivolumab	
Grade ≥ 2: Hold drug until resolution to baseline grade
 
Grade ≥ 3: Discontinue drug and start

CTCAE System/Organ/Class (SOC)	Event	Agent	Action
			corticosteroids until resolution to baseline grade and patient goes to event monitoring
General disorders and administration site conditions	Fatigue	Nivolumab	Grade 3: Hold drug until Grade 2 or better
Metabolism and nutrition disorders	Hyperglycemia	Nivolumab	Grade 4: Permanently discontinue nivolumab
Respiratory, thoracic and mediastinal disorders	Pneumonitis	Nivolumab	Grade ≥ 2 : Hold drug and start corticosteroids until resolution to baseline grade Grade ≥ 3 : Discontinue nivolumab and initiate treatment with high doses of corticosteroids and patient goes to event monitoring
	Cough	Nivolumab	Grade ≥ 2 : Hold drug and start corticosteroids until resolution to baseline grade Grade ≥ 3 : Discontinue nivolumab and initiate treatment with high doses of corticosteroids and patient goes to event monitoring
	Dyspnea	Nivolumab	Grade ≥ 2 : Hold drug until resolution to baseline grade
All other hematologic and non-hematologic	All other hematologic and non-hematologic	Nivolumab	Grade ≥ 2 : Hold nivolumab until resolution to Grade 1 or baseline, except for lymphopenia and leukopenia NOTE: Grade 3 lymphopenia or leukopenia do not require dose delay

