8.3 Discontinuation Criteria for Nivolumab

Treatment should be permanently discontinued for the following:

- Any Grade 2 drug-related uveitis or eye pain or blurred vision that does not respond to topical therapy and does not improve to Grade 1 severity within the re-treatment period OR requires systemic treatment
- Any Grade 3 non-skin, drug-related adverse event lasting >7 days, with the following exceptions for drug-related laboratory abnormalities, uveitis, pneumonitis, bronchospasm, hypersensitivity reactions, and infusion reactions, and endocrinopathies:
 - Grade 3 drug-related uveitis, pneumonitis, bronchospasm, hypersensitivity reaction, or infusion reaction of any duration requires discontinuation
 - Grade 3 drug-related endocrinopathies adequately controlled with only physiologic hormone replacement do not require discontinuation
 - Grade 3 drug-related laboratory abnormalities do not require treatment discontinuation except those noted below

- Grade 3 drug-related thrombocytopenia >7 days or associated with bleeding requires discontinuation
- Any drug-related liver function test (LFT) abnormality that meets the following criteria require discontinuation:
 - AST or ALT >8 x ULN
 - Total bilirubin >5 x ULN
 - Concurrent AST or ALT >3 x ULN and total bilirubin >2 x ULN
- Any Grade 4 drug-related adverse event or laboratory abnormality, except for the following events which do not require discontinuation:
 - Isolated Grade 4 amylase or lipase abnormalities that are not associated with symptoms or clinical manifestations of pancreatitis and decrease to < Grade 4 within 1 week of onset.
 - Isolated Grade 4 electrolyte imbalances/abnormalities that are not associated with clinical sequelae and are corrected with supplementation/appropriate management within 72 hours of their onset
 - Grade 4 lymphopenia or leucopenia
 - Grade 4 drug-related endocrinopathy adverse events, such as adrenal insufficiency, ACTH deficiency, hyper- or hypothyroidism, or glucose intolerance, which resolve or are adequately controlled with physiologic hormone replacement (corticosteroids, thyroid hormones) or glucose-controlling agents, respectively, may not require discontinuation after discussion with and approval from the Investigator [as allowed by protocol]
- Any dosing interruption lasting >6 weeks with the following exceptions:

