 - Dosing delays or interruptions to allow for prolonged steroid tapers to manage drug-related adverse events are allowed. Prior to re-initiating treatment in a subject with a dosing interruption lasting >6 weeks, the Investigator must be consulted. Tumor assessments should continue as per protocol even if dosing is interrupted or delayed
 - Dosing interruptions or delays lasting >6 weeks that occur for non-drug-related reasons may be allowed if approved by the Investigator. Prior to re-initiating treatment in a subject with a dosing interruption lasting >6 weeks, the Investigator must be consulted. Tumor assessments should continue as per protocol even if dosing is interrupted
- Any adverse event, laboratory abnormality, or intercurrent illness which, in the judgment of the Investigator, presents a substantial clinical risk to the subject with continued nivolumab dosing

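### Grade 4 drug-related pancreatitis: Section 8.2 says to restart nivolumab on improvement, Section 8.3 says to stop for good, and no readable text says which governs

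*Combined protocol and SAP*

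**What the plan says.** Section 8.0 applies the Section 8.2 table to events possibly, probably or definitely related to study drug. The table must be followed strictly in the first two cycles and is guidance after that.

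The pancreatitis row of Section 8.2 reads "Grade 3 or Grade 4, hold nivolumab until Grade 2 or better then reintroduce", followed by "If it recurs, the drug is discontinued and patient goes to event monitoring".

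Section 8.3 opens with "Treatment should be permanently discontinued for the following". Its list includes:

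- "Any Grade 4 drug-related adverse event or laboratory abnormality, except for the following events which do not require discontinuation". The exceptions are isolated enzyme abnormalities, isolated electrolyte abnormalities, lymphopenia or leucopenia, and controlled endocrinopathies. The enzyme exception applies only where the abnormality is not associated with "symptoms or clinical manifestations of pancreatitis and decrease to < Grade 4 within 1 week of onset".
- "Any Grade 3 non-skin, drug-related adverse event lasting >7 days", with exceptions that do not include pancreatitis.
- Any event that, in the investigator's judgment, "presents a substantial clinical risk to the subject with continued nivolumab dosing".

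Sections 8.2 and 8.3 do not refer to each other. Section 8.2 refers the reader to Appendix II, whose algorithm figures are not shown in the text available for this review.

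**The concern.** A drug-related Grade 4 clinical pancreatitis falls under both sections, and they give opposite instructions once it improves to Grade 2. One investigator following the table would re-dose; another following Section 8.3 would not. Re-dosing would expose the patient again to the drug held responsible for a life-threatening reaction, and patients with the same event could be handled differently.

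Two other provisions make re-dosing look unintended. Section 3.29d excludes anyone with a history of pancreatitis. Within the same row, a Grade 2 event must resolve before dosing resumes, with a three-week limit, yet a Grade 4 event may be re-dosed while still at Grade 2.

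The row also omits the Section 8.3 stop for Grade 3 non-skin events lasting more than 7 days.

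**Working it through.** **Comparing the texts.** Take a first drug-related clinical pancreatitis.

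| Situation | Section 8.2 row | Section 8.3 |
|---|---|---|
| Grade 4, improves to Grade 2 | Reintroduce; stop only on recurrence | Discontinue permanently |
| Grade 3, over 7 days, then Grade 2 | Reintroduce; duration not mentioned | Discontinue permanently |
| Grade 3, 7 days or less, then Grade 2 | Reintroduce | No stop under the duration rule |

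1. *Same events?* Yes. The table covers events at least possibly related to study drug, and the Section 8.3 rules cover drug-related events.
2. *Does an exception apply at Grade 4?* No. The only one close to pancreatitis is for isolated enzyme abnormalities, and it leaves out clinical pancreatitis.
3. *Is there a precedence rule?* None in the readable text. Section 8.0 does not mention Section 8.3. Its sentence on taking the greatest reduction concerns several adverse events at once, not two rules for one event. The readable part of Appendix II has neither a pancreatitis instruction nor a ranking.
4. *When does it bind?* In the strict period the table requires reintroduction while Section 8.3 requires stopping. Afterwards a site can follow Section 8.3 without breaching the table, but the table still recommends reintroduction. The maximum is 8 + 24 = 32 cycles (Section 7.11), so there are 32 − 1 = 31 dosing decisions after the first dose. The strict wording governs one of these (the Cycle 2 dose), or two if the timing of the event decides and the Cycle 3 dose is included. This counts decisions; it is not a risk.

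**How often it might arise.** Inputs are n = 39, the maximum accrual in Section 16.22, and the toxicity frequencies in Section 15.17. The expected number is n × p, and the chance of at least one case is 1 − (1 − p)^n.

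- Acute pancreatitis, listed among rare life-threatening toxicities at under 0.1%. With p = 0.001 as the upper bound: 39 × 0.001 = 0.039 expected, and 1 − 0.999^39 = 0.038.
- Pancreatitis without a stated grade, listed at 0.1% to under 1%. With p = 0.01 as the upper bound: 39 × 0.01 = 0.39 expected, and 1 − 0.99^39 ≈ 0.32. This is a ceiling for any grade. The shares that are Grade 4, or Grade 3 lasting more than 7 days, are not given.

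**Effect on the design.** The accrual-suspension rule in Section 16.42 counts patients with a Grade 4 or higher related non-hematologic event, so the patient counts once whether or not re-dosed.

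**The case against.** The best defense is structural: Section 8.2 sets delays, and Section 8.3 sets stops on top of them. The catch-all and dyspnea rows support this. Both say to hold from Grade 2 upward and name no stop, so if the table displaced Section 8.3, the Grade 4 stop there would be nearly empty. On this view the pancreatitis row is a drafting slip.

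That may well explain how the wording arose, but it does not settle it. The table contains stops of its own, including permanent ones for liver tests and, in the same organ class as pancreatitis, "Grade 3 or 4 despite maximal supportive care: Discontinue drug and start corticosteroids until resolution to baseline". The catch-all row can be read alongside Section 8.3. The pancreatitis row cannot, because it names Grade 4, orders reintroduction and gives recurrence as the trigger for stopping.

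There are also safeguards. The row asks for consultation with the principal investigator on Grade 3 or higher amylase or lipase abnormalities. Serious Grade 3 to 5 events are reported within 24 hours (Section 10.41). Treatment starts at three campuses of one institution (Section 6.9a). An investigator may stop for substantial clinical risk. These lower the chance of harm or of divergent handling, but none says which rule applies by default.

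Three points stand in part. The row's silence on prolonged Grade 3 events can be read as leaving Section 8.3 to apply, so that gap is weaker than the Grade 4 contradiction. Adding pancreatitis to the Section 8.3 exceptions would equally remove the conflict, and that choice is clinical. And because the Appendix II figures could not be read, the absence of a governing instruction is established only for the readable text.

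**Conclusion.** The concern holds. As written, Sections 8.2 and 8.3 require opposite actions after a first drug-related Grade 4 clinical pancreatitis that improves to Grade 2, and nothing readable resolves it. The contradiction is sharpest in the first two cycles, when the table is strict.

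The event is rare and the consequence serious: fewer than 0.04 expected life-threatening cases in 39 patients, assuming the Section 15.17 frequency applies to this population. The matter is patient safety and consistent dosing only. It does not touch the response endpoint, the decision rules at 12 and 35 patients, or the accrual-suspension count. It should be fixed, because the error is clear and the correction nearly free.

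**What to change.** Align the row with what Section 8.3 already requires:

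- In the Section 8.2 pancreatitis row, remove Grade 4 from the reintroduction line and add: *Grade 4, or Grade 3 lasting >7 days: permanently discontinue per 8.3; patient goes to event monitoring.*
- In Section 8.0, add: *Where 8.3 requires permanent discontinuation, 8.3 prevails over the 8.2 table in all cycles.* This also settles any other row that overlaps with Section 8.3.

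If the sponsor does intend rechallenge after Grade 4 pancreatitis, it should instead add and justify an explicit exception in Section 8.3. The stricter option is preferable given the exclusion of patients with a history of pancreatitis.

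The cost is a short text amendment. A patient who recovers from Grade 4 pancreatitis could not be re-treated, which Section 8.3 already rules out. Sample size, endpoints and analysis do not change. The Appendix II algorithms should be checked for consistency at the same time.

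### For drug-related clinical pancreatitis, section 8.2 instructs restarting nivolumab after Grade 3-4, while section 8.3 calls for permanent discontinuation at Grade 4 and at Grade 3 beyond 7 days, with no stated precedence

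*Combined protocol and SAP*

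**What the plan says.** Section 8.0 governs events at least possibly related to study drug. It tells sites to "strictly follow the modifications in this table for the first" two cycles, and adds: "Thereafter, these modifications should be regarded as guidelines".

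The pancreatitis row of section 8.2 has two clinical branches:

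- For Grade 2: "Grade 2: Hold nivolumab until resolution, maximum 3 weeks". A longer hold ends treatment.
- For the higher grades: "Grade 3 or Grade 4, hold nivolumab until Grade 2 or better then reintroduce". Treatment ends only on recurrence.

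The same row deals separately with amylase or lipase elevations that have no clinical picture of pancreatitis, and asks that the PI be consulted for enzyme abnormalities of Grade 3 or more.

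Section 8.3 lists the events for which treatment should be permanently discontinued. Two entries matter here:

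- "Any Grade 3 non-skin, drug-related adverse event lasting >7 days", with named exceptions.
- "Any Grade 4 drug-related adverse event or laboratory abnormality, except for the following events which do not require discontinuation".

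The only Grade 4 exception that concerns the pancreas is "Isolated Grade 4 amylase or lipase abnormalities that are not associated with symptoms or clinical manifestations of pancreatitis", and even that requires the value to fall below Grade 4 within a week.

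**The concern.** Sections 8.2 and 8.3 address the same patient and give opposite instructions. A site that reads only the pancreatitis row would re-dose after drug-related Grade 4 pancreatitis, possibly while the pancreatitis is still Grade 2. A site that reads 8.3 would stop for good.

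The protocol itself treats pancreatitis as a serious risk. Section 3.29d excludes patients with a history of it, and section 15.17 places acute pancreatitis among the life-threatening toxicities. What is at stake is patient safety and consistent handling across the three treating sites, not the efficacy analysis.

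**Working it through.** **Step 1. Compare the two sections case by case (drug-related events).**

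| Case | Section 8.2 row | Section 8.3 | Result |
|---|---|---|---|
| Clinical pancreatitis, Grade 4 | Hold, restart at Grade 2 or better | Permanent stop | Conflict |
| Clinical pancreatitis, Grade 3, more than 7 days | Hold, restart at Grade 2 or better | Permanent stop | Conflict |
| Clinical pancreatitis, Grade 3, 7 days or less | Hold, restart at Grade 2 or better | Duration rule not triggered | No conflict with 8.3 |
| Isolated Grade 3 enzyme elevation, no symptoms | No delay needed | Laboratory exception | No conflict |

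Isolated Grade 4 enzyme elevations have their own conditions in 8.3 and are outside this point.

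**Step 2. Can an exception reconcile them?** The Grade 3 exceptions in 8.3 cover laboratory abnormalities, uveitis, pneumonitis, bronchospasm, hypersensitivity and infusion reactions, and endocrinopathies. Pancreatitis is not among them. The Grade 4 enzyme exception expressly leaves out clinical pancreatitis. Attribution does not separate the sections either: 8.0 applies the table to events at least possibly related to treatment, and these two 8.3 criteria concern drug-related events.

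**Step 3. Is precedence stated?** The one tie-break in 8.0 is for several concurrent adverse events, not for two rules about one event. The readable text of 8.0 to 8.3 and Appendix II contains no precedence statement. The Appendix II algorithms are figures not shown; their readable titles include none for pancreatitis, and nothing is concluded from the figures themselves.

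**Step 4. Is the wording of this row special?** Yes. The liver entries permit resumption. The "Hold nivolumab until resolution to Grade 1 or baseline, except for lymphopenia and leukopenia" instruction in the catch-all row, like the fatigue and dyspnea rows, sets only a condition for ending the hold. Section 8.3 can be laid over those without contradiction. The pancreatitis row alone directs a restart.

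**Step 5. Is the row consistent with itself?** Grade 2 must resolve, within 3 weeks, before dosing continues. After Grade 3 or 4, dosing restarts on reaching Grade 2. The more severe event therefore has the looser restart threshold.

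**Step 6. How often could this arise?** Inputs: maximum accrual 39 (section 16.22); pancreatitis listed at 0.1% to under 1%, and acute pancreatitis at under 0.1% in the list limited to life-threatening toxicities (section 15.17).

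- Expected cases, any grade, whole study: 39 × 0.001 = 0.039; 39 × 0.01 = 0.39, an upper limit that is not reached.
- Chance of at least one, any grade: 1 − 0.999^39 = 3.8%; 1 − 0.99^39 = 32.4%, again not reached.
- Acute pancreatitis: under 39 × 0.001 = 0.039 cases; chance of at least one under 3.8%.
- Strict period of the table: 2 × 14 = 28 days.

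The firm conflict needs a drug-related Grade 4 or prolonged Grade 3 event within that 28-day period, so its expected count is well below the any-grade figures.

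**The case against.** The strongest reply is that the sections are meant to be read in sequence: 8.2 is headed as delay criteria and 8.3 as discontinuation criteria, so a patient stopped under 8.3 has nothing left to restart. That is the natural and safer reading. It remains an inference, because 8.2 contains stops of its own, including in the pancreatitis row, so the headings do not establish a hierarchy.

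A reader might infer that a site facing Grade 4 pancreatitis in cycles 1-2 is bound to break one of two rules. The documents do not support that. Section 8.3 says treatment should be stopped, and its last entry lets the investigator stop in any cycle for an event that poses substantial clinical risk. The PI consultation in the 8.2 row adds a further check where the enzymes reach Grade 3. A safe course is always open, but these safeguards do not remove the instruction to reintroduce.

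The strict period may also be narrower than it looks. If strictness attaches to the dosing decisions in cycles 1-2, an event after the cycle 2 dose leads to a cycle 3 decision, when the table is guidance. The strict clash would then concern essentially one restart, the cycle 2 dose. Section 8.0 does not settle this.

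Finally, a reader might take 32.4% as the chance that the conflict arises. It is not: it is a ceiling for pancreatitis of any grade at any time on study.

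**Conclusion.** The contradiction is in the text and should be corrected. It covers two cases of drug-related clinical pancreatitis: Grade 4, and Grade 3 lasting more than 7 days. It is firmest in cycles 1-2; from cycle 3 the table is guidance and 8.3 can simply be followed, though still without a stated rule. The mismatch between the Grade 2 and Grade 3-4 restart thresholds is a second, smaller fault in the same row.

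The practical size is very small, well below 0.04 to under 0.4 expected cases in 39 patients. This assumes that the general nivolumab rates in section 15.17 carry over to this population, from which patients with prior pancreatitis are excluded. Objective response rate, sample size and power are not affected. The case for acting is the safety consequence of a literal reading and the low cost of removing it.

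A reader might go further and infer that the stops in 8.2 should always survive the exceptions in 8.3. That does not follow from this point. Section 8.2 stops permanently for Grade 4 hyperglycemia, while 8.3 may allow continuation for controlled Grade 4 glucose intolerance after Investigator approval. That is a separate clinical decision, which the pancreatitis conflict does not settle.

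**What to change.** Add one sentence to section 8.0 or 8.2: the permanent-discontinuation criteria in 8.3 apply in all cycles and override any hold or reintroduce instruction in 8.2.

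Replace the Grade 3-4 part of the pancreatitis row with:

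> Grade 4, or Grade 3 lasting >7 days: permanently discontinue per 8.3. Grade 3 lasting 7 days or less: hold until resolution, maximum 3 weeks, as for Grade 2; if it recurs, discontinue.

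The restart threshold for short Grade 3 events is a clinical choice for the sponsor to confirm; the wording above aligns it with the existing Grade 2 rule. If the sponsor does intend rechallenge after Grade 4 or prolonged Grade 3 pancreatitis, it should be a named exception in 8.3 with its conditions.

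The cost is a protocol wording change. No design, sample size or analysis text needs to change.

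### Section 8.2, Pancreatitis row: restart is allowed at a lower bar after a short Grade 3 episode than after a Grade 2 episode, and the Grade 4 instruction contradicts Section 8.3

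*Combined protocol and SAP*

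**What the plan says.** The Pancreatitis row of Section 8.2 gives these instructions:

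- Grade 2: "Grade 2: Hold nivolumab until resolution, maximum 3 weeks". Beyond 3 weeks the drug is stopped and the patient moves to event monitoring.
- Grade 3 or 4: "Grade 3 or Grade 4, hold nivolumab until Grade 2 or better then reintroduce".
- Afterwards: "If it recurs, the drug is discontinued and patient goes to event monitoring".
- Enzyme elevations of Grade 3 or higher without clinical pancreatitis need no delay, but the PI should be consulted about amylase or lipase abnormalities of Grade 3 or higher.

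Section 8.3 lists permanent stops. They include "Any Grade 3 non-skin, drug-related adverse event lasting >7 days" (with exceptions that do not name pancreatitis) and "Any Grade 4 drug-related adverse event or laboratory abnormality", outside four exceptions. The nearest of the four is "Isolated Grade 4 amylase or lipase abnormalities that are not associated with symptoms or clinical manifestations of pancreatitis", and those abnormalities must also fall below Grade 4 within a week.

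Section 8.0 applies the table to events at least possibly related to treatment. It makes the table strict for the first two cycles and a guideline after that. Section 8.1 rules out dose reduction.

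**The concern.** Two things look wrong. First, within one row the more severe episode has the looser restart rule: Grade 2 is a reason to hold if the episode began there, but a permitted restart level if the episode began at Grade 3. Second, the row tells the site to reintroduce the drug after Grade 4, where Section 8.3 ends treatment.

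The stake is patient safety. In the first two cycles the table binds strictly and no reduced dose exists. A restart there is the full 240 mg, given while pancreatitis is at a grade that the same row treats as a reason to withhold the drug. Sites could also handle the same patient differently. The effect on the response endpoint is immaterial.

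**Working it through.** The plan states no figure on this point. The check sets the two sections side by side, then sizes the affected group.

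**Grade-by-grade reading (drug-related clinical pancreatitis)**

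| Episode | Section 8.2 | Section 8.3 | Combined |
|---|---|---|---|
| Grade 2 | Hold to resolution; stop after 3 weeks | No stop for this grade and duration | Consistent |
| Grade 3, 7 days or less | Hold to Grade 2, then reintroduce | No stop for this grade and duration | Restart allowed at a grade the row itself holds |
| Grade 3, more than 7 days | Hold to Grade 2, then reintroduce | Permanent stop | Section 8.3 ends treatment if it prevails |
| Grade 4 | Hold to Grade 2, then reintroduce | Permanent stop; no exception fits | Contradiction |

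No text says which section prevails.

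**Comparison with other rows of Section 8.2.** Fatigue uses a similar release rule, "Grade 3: Hold drug until Grade 2 or better", but Grade 2 fatigue triggers no hold, so that row is coherent. The same is true of AST/ALT and bilirubin when the baseline is Grade 1: the hold starts at Grade 3 and ends at Grade 2. Diarrhea, colitis, pneumonitis and cough hold at Grade 2 and discontinue at Grade 3. The catch-all row holds from Grade 2 and releases at Grade 1 or baseline. Pancreatitis is the only row whose release grade is also a hold grade.

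**Size: inputs**

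- Maximum accrual: 39 (Section 16.22).
- Pancreatitis: 0.1% to <1%. Acute pancreatitis: <0.1%, in a list limited to life-threatening events (both Section 15.17).
- Schedule: 8 cycles of 14 days, then up to 24 of 28 days (Section 7.11).
- Assumed, not in the documents: 10% to 50% of cases are Grade 3 for 7 days or less and still Grade 2 when a dose is due.

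**Cases of any grade**

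- Low: 39 × 0.001 = 0.039.
- High (upper bound, adding both listings): 39 × (0.01 + 0.001) = 0.429.

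**Chance of at least one case**

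- Low: 1 − 0.999^39 = 0.038.
- High: 1 − 0.989^39 = 0.350.

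**Patients in the short Grade 3 gap, all treatment**

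- Low: 0.039 × 0.10 = 0.0039.
- High: 0.429 × 0.50 = 0.2145.

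**Share of treatment in which the table binds strictly**

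- Maximum treatment: 8 × 14 + 24 × 28 = 112 + 672 = 784 days.
- First two cycles: 2 × 14 = 28 days; 28/784 = 3.6% of days (2/32 = 6.25% of cycles).
- Onset spread evenly over 784 days, low end: 0.0039 × 0.0357 = 0.00014 patients.
- All onsets in the first two cycles, high end: 0.2145 patients.

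**Grade 4 contradiction.** If the life-threatening acute pancreatitis listing is taken as a proxy for Grade 4 (an assumption), fewer than 39 × 0.001 = 0.039 patients are expected.

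**The case against.** The best defence has four parts.

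- **Section 8.3 prevails.** A stop rule read together with a delay rule ends treatment before any restart arises. That is a sensible reading, and it would settle Grade 4 and Grade 3 beyond 7 days. But it is not written, the row names Grade 4 expressly, and Section 8.0 orders strict adherence to the table early on. It also leaves the short Grade 3 case open.
- **The row does not compel a dose at Grade 2.** Full resolution also satisfies the release condition, and a site could apply the Grade 2 line to an improving patient. That is so, but the row goes straight from reaching Grade 2 to reintroduction, so a site that re-doses then is also following it.
- **Safeguards exist.** These are discontinuation on recurrence, PI consultation for enzyme abnormalities of Grade 3 or higher, amylase and lipase testing each cycle, guideline status after two cycles, and the investigator's stop for anything that "presents a substantial clinical risk to the subject with continued nivolumab dosing", which applies from the start. A hold is also limited by the 6-week interruption rule. These reduce the risk, but none sets the restart grade.
- **Harm is not shown, and one rechallenge may be deliberate in this population.** The first half stands: the protocol does not reproduce the CTCAE definition of Grade 2 pancreatitis, so the clinical harm cannot be sized from it. A deliberate rechallenge policy would still not explain a stricter rule for the milder episode.

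The size estimate is also rough. The 10% to 50% fraction has no source in the documents. The upper bound adds a life-threatening category to an estimate about short Grade 3 episodes. And 39 includes an allowance for patients who cancel before treatment. The last two overstate the size.

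**Conclusion.** Both points hold as a matter of text: the restart threshold is inverted for Grade 3 pancreatitis lasting 7 days or less, and the Grade 4 instruction contradicts Section 8.3. The priority is low. Well under one patient is expected to be affected: 0.004 to less than 0.22 over all treatment, depending on the Section 15.17 frequencies and the assumed 10% to 50% fraction. For the strictly binding first two cycles the range is about 0.0001 to less than 0.22, depending on onset timing, which the documents do not give. Excluding patients with a history of pancreatitis (Section 3.29d) may lower this further. Confidence is medium, because the clinical weight of residual Grade 2 disease cannot be judged from the protocol. Sample size, significance level and power are unaffected.

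**What to change.** Replace only the Grade 3/4 line of the Pancreatitis row, along these lines:

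*Grade 3: hold to full resolution, for no longer than 3 weeks (stop if Grade 3 itself persists beyond 7 days, per Section 8.3). If not resolved by 3 weeks, or if pancreatitis returns after restart, stop nivolumab and move to event monitoring. Grade 4: stop permanently, per Section 8.3.*

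Leave the Grade 2 lines, the recurrence line, the exemption for enzyme elevations without symptoms and the PI-consultation line as they are. Nothing then changes for Grade 2 episodes or isolated enzyme elevations. The new text repeats the recurrence rule, which is harmless and keeps it attached to Grade 3.

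The cost is one line in the next amendment. The 3-week limit is new for Grade 3, so a rare patient recovering from a short Grade 3 episode may be held longer or stopped.
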